#### Exclusion Criteria

A person will be excluded from the study if he/she:

- Has never worn contact lenses before.
- Has any systemic disease affecting ocular health.
- Is using any systemic or topical medications that will affect ocular health.
- Has any ocular pathology or severe insufficiency of lacrimal secretion (moderate to severe dry eyes) that would affect the wearing of contact lenses.
- Has persistent, clinically significant corneal or conjunctival staining using sodium fluorescein dye.

- Has any clinically significant lid or conjunctival abnormalities, active neovascularization or any central corneal scars.
- Is aphakic.
- Has strabismus/amblyopia.
- Has undergone corneal refractive surgery.
- Is pregnant, lactating or planning a pregnancy.
- Is participating in any concurrent clinical or research study.

## 7.2 Study Materials

### 7.2.1 Contact lens

Subjects will be randomized to receive the Test and Control lenses bilaterally potentially as an unmatched pair (with regards to power), per a predetermined randomization schedule. The daily disposable/single use lenses used in this study will be provided by the Sponsor. Details of the contact lenses are shown in Table 1.

**Table 1: Study lenses**

	Test Orion	Control Gemini [REDACTED]
Labelling	Masked Investigational	Masked Investigational
Manufacturer	Coopervision, Inc.	Coopervision, Inc.
Material	riofilcon A with DAB	riofilcon A
Water Content	8.60	8.60
Base curve (mm)	14.00	14.00
Power (D)	-1.00 to -6.00 (0.25 steps)	-1.00 to -6.00 (0.25 steps)

### 7.2.2 Contact Lens care

No contact lens care is required for this study as lenses are to be worn for a single day only.

### 7.2.3 Storage of Lenses and Lens Care Solutions

The study materials must be stored in a secured area. All lenses and lens care solutions should be stored at controlled room temperature (59-86°F).

#### **7.2.4 Clinical Supply Inventory**

The investigator must keep an accurate accounting of the study product during the study. A detailed inventory must be completed for study supplies. The study supplies are to be used in accordance with the protocol by subjects who are under the direct supervision of an investigator.

#### **7.2.5 Disposal of Consumables**

This study dispenses consumables (lenses) to participants for use during the study. Subjects will be asked to retain their lens foils each day for return to the study investigator, for lens accountability purposes. Additionally, study lenses worn by participants at the 2-week follow-up visits will be collected and stored in either an unbuffered or phosphate buffered (not borate) saline for return to the Sponsor.

#### **7.2.6 Masking and Control of Study Materials**

The contact lenses coding will be masked to both the investigator and subject.

#### **7.2.7 Ordering and Accountability of Study Materials**

The Test and Control lenses will be provided by the Sponsor. The investigator must complete an accurate accounting of the study product at the completion of the study. A detailed inventory must be completed for study supplies. All unused and used materials will be returned to the Sponsor at the end of the study unless the investigator is otherwise directed by the study Sponsor.

### **7.3 Visit Schedule and Procedures**

---

#### **7.3.1 Visit 1a: Baseline / Screening Visit**

##### *Procedures to be Performed*

The following evaluations will be performed to assess eligibility according to the Inclusion and Exclusion Criteria at the baseline visit only:

- The patient is expected to attend the baseline visit not wearing their habitual contact lens products.
- The subject will be required to read and sign an Informed Consent Form prior to enrolment. When the subject has signed the consent form, the subject will be considered enrolled onto the study.
- Habitual lens wearing time (average, maximum, average comfortable). Also, habitual type of comfort / re-wetting drops and frequency of use, if any, will be recorded.

- Sphero-cylindrical refraction will be conducted and baseline monocular and binocular High Illumination High Contrast (**HIHC**) and High Illumination Low Contrast (**HILC**) logMAR distance visual acuities recorded.
- Slit lamp biomicroscopy will be assessed according to the guidelines set out in the CVI Grading scales [REDACTED]
- The investigator will confirm that the patient meets the criteria set out in the inclusion criteria.

### 7.3.2 Visit 1b: Dispensing Visit (Pair 1)

*Dispensing visit may occur on same day as Visit 1a. If Visit 1b is conducted on a different day to Visit 1a, slit lamp biomicroscopy should be conducted again to confirm eligibility.*

- HVID (mm) and palpebral aperture size (mm) measurements using slit lamp oculars.
- The first study pair of contact lenses will be selected by the investigator according to the randomization table [REDACTED] insertion by the subjects. Subjects will be dispensed the lens power nearest to their refractive error requirement.
- Lenses should be allowed to settle for 10 minutes.
- An initial fit assessment will be made to ensure lens fit is acceptable (Y/N). The subject should be discontinued and exited if the lens fit is found unacceptable and the primary reason for poor fit recorded on the CRF and video footage of the fit collected.
- Monocular spherical over-refraction (SOR) will be conducted to determine if a different lens power is required.
- Monocular and binocular **HIHC** and **HILC** distance logMAR visual acuities will be recorded (SOR will be used if the subject is wearing monovision).
- Final lenses will be inserted and allowed to settle for a further 10 minutes, if applicable.

- [REDACTED]

- [REDACTED]
- [REDACTED]
- [REDACTED]
- [REDACTED]
- [REDACTED]
- [REDACTED]
- [REDACTED]
- [REDACTED]
- [REDACTED]

- Lens surface will then be assessed and graded after settling per guidelines detailed in the CVI grading scales ( [REDACTED] )
  - [REDACTED]
  - Wettability (0-4 scale)
  - [REDACTED]
  - [REDACTED]
- Lens fit will then be assessed and graded according to the guidelines detailed in CVI Grading scales ( [REDACTED] ).
  - Lens centration (0.1mm steps)
  - [REDACTED]
  - Post-blink movement (0.1mm steps)
  - Mobility rating (0.50 steps)
  - Overall lens movement (-2 to +2 scale)
  - Overall lens fit acceptance and investigator reason, if unacceptable (0.25 steps). Video will be recorded in the event of poor fit. Video will be recorded in the event of poor fit.
- The subject will be instructed to wear the study lenses for a minimum of 8 hours per day / 6 days per week.
- The subject will be dispensed adequate lenses (including spares) to last them until the next study visit.
- The subject will be discharged and scheduled to return for Visit 2 within the required study visit window.

### 7.3.3 Visit 2: Two-Week Follow-up Pair 1 (-1/+4 days) & Dispensing Pair 2

*Subjects will be asked to wear lenses for **at least 3 hours** prior to the visit appointment.*

- Subjective responses will be collected per the Final Questionnaire [REDACTED] including:
  - Overall satisfaction (7-point Likert scale)
  - Comfort satisfaction & comfort rating (7-point Likert & 100-point scales)
  - [REDACTED]
  - [REDACTED]
  - [REDACTED]
  - [REDACTED]
  - [REDACTED]
  - [REDACTED]
  - [REDACTED]

- [REDACTED]
  - Lens handling (7-point Likert & 100-point scales)
  - [REDACTED]
  - [REDACTED]
  - Lens holding/handling (5-point Likert scales)
  - Vision (7-point Likert & 100-point scales)
- The following information will be collected from the subject by the investigator:
    - Wear time at visit (hours).
    - Average time of insertion and removal during previous week, i.e. average time (hours).
    - Maximum wear time during previous week (hours).
    - Average time of day lenses become uncomfortable, if at all, i.e. average comfortable wear time (hours).
    - Use and frequency of comfort / re-wetting drops during past week (if any).
  - Monocular and binocular **HIHC** and **HILC** distance logMAR visual acuities will be recorded (a spherical over-refraction will be performed for the distance eye and recorded first if the subject is wearing monovision).
  - Lens surface will then be assessed and graded per guidelines detailed in the CVI grading scales [REDACTED]
    - [REDACTED]
    - Wettability (0-4 scale)
    - [REDACTED]
    - [REDACTED]
  - Lens fit will then be assessed and graded according to the guidelines detailed in CVI Grading scales [REDACTED]
    - Lens centration (0.1mm steps)
    - [REDACTED]
    - Post-blink movement (0.1mm steps)
    - Mobility rating (0.50 steps)
    - Overall lens movement (-2 to +2 scale)
    - Overall lens fit acceptance and investigator reason, if unacceptable (0.25 steps). Video will be recorded in the event of poor fit.
  - The lenses will be removed and stored in either an unbuffered or phosphate buffered (not borate) saline for return to the Sponsor.

- Slit lamp biomicroscopy will be assessed according to the CVI approved study biomicroscopy CRF [REDACTED]

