### 2.1 Study Hypothesis

---

The primary hypothesis is that there will be no difference in vision performance between the Orion Test lens and the Gemini Control lens.

The secondary hypothesis is that there will be no difference in performance between the Orion Test lens and the Gemini Control lens for any of the secondary variables.

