**Table 4: Secondary variable (comfort) sample size calculation**

Non-inferiority margin for comfort	Mean individual standard deviation	Sample size, Power 80% (p = 0.05)
-0.75	1.3	53

Consequently, a sample size of approximately 60 completing subjects is sufficient for this study.

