## 10.2 Statistical analysis

---

Summary statistics will be produced (e.g. mean, standard deviation). Paired t-test will be used to compare slit lamp biomicroscopy, lens fit and subjective scores between study lens types. Repeated Measures Analysis of Variance (ANOVA) or paired analysis will be used to compare the variables between study visits. The critical alpha level for statistical significance will be set at  $p \leq 0.05$ , with adjustment for multiple comparisons.

All participants who were evaluated will be used in the analysis. In the event of missing data, individual data points will be excluded in the analysis and not extrapolated from the collected data.

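### If 0 is the optimum on the -2 to +2 lens-movement scale, the planned paired t-test on that item cannot detect a lens that departs from it in both directions about equally

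*Combined protocol and SAP*

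**What the plan says.** Section 2 lists lens fit among the secondary variables. Section 2.1 states for these that "there will be no difference in performance between the Orion Test lens and the Gemini Control lens for any of the secondary variables". Section 3.1 gives the aim as matching the clinical performance of the Control lens.

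Sections 7.3.2 to 7.3.4 list the item "Overall lens movement (-2 to +2 scale" at each fit assessment: dispensing of Pair 1, follow-up of Pair 1, dispensing of Pair 2 and follow-up of Pair 2. Each of these assessments also records "Overall lens fit acceptance and investigator reason, if unacceptable (0.25 steps", together with centration and mobility. Post-blink movement is listed at most of them in the visible text. The meaning of -2, 0 and +2 belongs to the grading scales in Appendix 4, whose figures are not shown.

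Section 10.2 states: "Paired t-test will be used to compare slit lamp biomicroscopy, lens fit and subjective scores between study lens types". It also plans summary statistics, naming the mean and standard deviation as examples, and an alpha of 0.05 with an unspecified adjustment for multiple comparisons. It gives no recoding, absolute deviation or categorical analysis for the movement item.

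**The concern.** A scale that runs equally far below and above zero usually describes two opposite departures from a reference value. The same visit lists grade wettability from 0 to 4, which is one-directional, so the signed range for movement looks deliberate. If 0 is the optimum, quality on this item is the distance from 0. A paired t-test of the recorded score compares signed means instead. A lens graded below 0 on some eyes and above 0 on as many others has the same mean as a lens graded 0 on every eye.

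Because the stated hypothesis is one of no difference, an insensitive test favours it. A non-significant signed mean could be taken as evidence of matched movement when it says little about how many eyes are away from the optimum.

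**Working it through.** The plan states no figure, standard deviation or margin for lens movement, so there is nothing of its own to reproduce. What can be checked is the mechanism.

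**Inputs from the documents**
- Scale of -2 to +2 (sections 7.3.2 to 7.3.4).
- Paired t-test (section 10.2).
- Alpha 0.05 (section 10.2).
- n = 60 pairs, from "a sample size of approximately 60 completing subjects is sufficient for this study" (section 10.1).

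**Assumptions**
- 0 is the optimum, and the recorded score is analysed as it stands.
- The test is two-sided at 0.05, before any multiplicity adjustment.
- There is one score per subject per lens, with no correlation within subject.
- Every score distribution below is assumed.

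**Formulas.** With independent scores, the mean paired difference is d = mean(Test) − mean(Control), and its SD is s = √(var(Test) + var(Control)). The noncentrality is λ = (d/s) × √60. The test rejects when |t| exceeds the 97.5% point on 59 degrees of freedom. For the absolute score, var|X| = E(X²) − (E|X|)².

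**Control**, with probabilities at -2, -1, 0, +1, +2 of .02/.08/.80/.08/.02:
- E(X) = 0
- E(X²) = 2(.02×4 + .08×1) = 0.32
- E|X| = 2(.02×2 + .08×1) = 0.24
- var|X| = 0.32 − 0.24² = 0.2624

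**Scenario (a), Test** .10/.20/.40/.20/.10:
- E(X) = 0
- E(X²) = 2(.10×4 + .20×1) = 1.20
- E|X| = 2(.10×2 + .20×1) = 0.80
- var|X| = 1.20 − 0.80² = 0.56
- Signed: d = 0, so λ = 0 and the test rejects only at its nominal 5%.
- Absolute: d = 0.80 − 0.24 = 0.56; s = √(0.56 + 0.2624) = 0.907; λ = (0.56/0.907) × √60 ≈ 4.78.

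Rejection rates from 20,000 simulated trials per scenario, with the same Control throughout:

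| Scenario | Test distribution | Test off 0 (Control 20%) | Mean absolute score (Control 0.24) | Signed test rejects | Absolute-score test rejects |
|---|---|---|---|---|---|
| (a) symmetric | .10/.20/.40/.20/.10 | 60% | 0.80 | 4.7% | 99.7% |
| (b) milder symmetric | .05/.15/.60/.15/.05 | 40% | 0.50 | 5.0% | 64.9% |
| (c) slightly asymmetric | .10/.25/.40/.20/.05 | 60% | 0.75 | 15.8% | 99.2% |
| (d) mostly one-directional | 0/.10/.50/.30/.10 | 50% | 0.60 | 88.0% | 89.5% |

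**Sensitivity to the Control distribution.** Take Control as .025/.10/.75/.10/.025 and Test as in (a). Then E|X| for Control is 2(.025×2 + .10×1) = 0.30 and E(X²) is 2(.025×4 + .10×1) = 0.40. So var|X| = 0.40 − 0.30² = 0.31, d = 0.80 − 0.30 = 0.50 and s = √(0.56 + 0.31) = 0.93. The absolute-score test rejects about 98% of the time and the signed test 5%.

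**What the planned summary table would show there.** The SD of the signed score is √0.40 = 0.63 for Control and √1.20 = 1.10 for Test, which is 1.10/0.63 − 1 ≈ 0.73, or about 73% larger.

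The loss of sensitivity is complete when the Test departures balance, large when they nearly balance (c), and absent when they run mainly one way (d).

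**The case against.** A reader might infer that a worse-fitting lens could pass through this trial looking identical to Control. The documents do not support that.

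- **Fit quality is also graded directly.** The overall fit acceptance grade is taken at the same assessments and is itself a lens-fit score under section 10.2. Mobility, centration and, at most assessments, post-blink movement add to it.
- **Fit failures are recorded.** At each dispensing, "The subject should be discontinued and exited if the lens fit is found unacceptable", with the primary reason recorded and video collected.
- **The spread would be visible.** In the scenario with SDs of 0.63 and 1.10, the planned summary statistics would show the difference although the means agree.
- **Balanced departures are an assumed worst case.** Nothing in the documents predicts them. Table 1 gives both lenses the same dimensions and powers, and the materials differ only by the added DAB. A mostly one-directional shift is found equally well by the signed test.
- **The anchors are not shown.** That 0 is the optimum, and that the two ends mean too little and too much movement, are inferences. So is the use of the raw score, since section 10.2 never says signed. Appendix 4 may define how the item is read.
- **The absolute score has its own blind spot.** Control mostly at -1 and Test mostly at +1 would give equal absolute scores. A signed comparison tests whether Test moves more or less than Control, which bears on the aim of matching it.

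All of this stands, and it limits the point to one item. It also rules out replacing the signed test. It does not make the signed mean informative about two-directional misfit. The acceptance grade is an overall judgement and does not analyse movement. The exit check comes before the movement grading, so subjects who fail it contribute no movement score for that lens. The paired comparison then rests on subjects who passed, among whom moderate departures in either direction could still occur.

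**Conclusion.** The point holds for this one item, on the assumptions that 0 is the optimum and that the recorded score enters the t-test unchanged. With 60 pairs, the signed comparison rejects at about its nominal 5% when Test departures are balanced, even with 60% of Test scores off-optimum against 20% for Control. The absolute score rejects 64.9% to 99.7% of the time in the symmetric scenarios. Slight asymmetry raises the signed test only to 15.8%. With a mostly one-directional shift the two tests are equivalent for practical purposes.

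The percentages illustrate the mechanism and do not predict this trial. They use unadjusted alpha, so the planned multiplicity adjustment would lower the power of both tests. Positive correlation between a subject's two absolute scores would raise the power of the absolute-score test. It would leave the balanced signed mean difference at zero.

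The consequence is modest: one item of one secondary variable in a feasibility study, with no bearing on the acuity analysis or the sample size. It is still worth correcting, because the plan's hypothesis of no difference invites a reading that this test cannot support.

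**What to change.** In section 10.2:

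1. Keep the paired comparison of the signed movement score, labelled as a comparison of direction.
2. Add a paired comparison of the absolute deviation from the optimum defined in Appendix 4, or of the proportion of scores graded at that optimum. If Appendix 4 places the optimum elsewhere than 0, take the deviation from that value.
3. Tabulate the full -2 to +2 distribution by lens.
4. State that matched movement will not be concluded from the signed mean alone.

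This takes a few lines of text and needs no new data, visits or subjects. The cost is one additional comparison within the planned multiplicity adjustment.

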### 7.1 Participants

---

Up to 70 subjects will be enrolled and dispensed in order for approximately 60 subjects to complete the study. Each subject will be given a unique ID number. ID numbers will not be reused in event of screen failure or discontinuation. Additionally, all subjects must meet the study inclusion and exclusion criteria listed below.

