#### Inclusion criteria

A person is eligible for inclusion in the study if he/she:

- Is at least 18 years of age and has full legal capacity to volunteer.
- Is no greater than 55 years of age.
- Has read and understood the information consent letter.
- Is willing and able to follow instructions and maintain the appointment schedule.
- Is an adapted soft contact lens wearer having worn lenses for a minimum of 4 weeks prior to the study.
- Has spectacle cylinder  $\leq 1.00D$  in both eyes.
- Has spherical contact lens power requirement between  $-1.00D$  and  $-6.00D$  in both eyes.
- Has manifest refraction visual acuities (VA) equal to or better than logMAR equivalent of 20/20 in each eye.
- Wears CLs in both eyes (monovision acceptable, but not monofit)
- Has clear corneas and no active ocular disease.
- Has not worn lenses for at least 12 hours before the examination.
- Is willing to wear the study contact lenses for a minimum 8 hours per day/6 days per week

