### Dispensing Visit (Pair 2)

- The subject will undergo a saline washout.
- The second study pair of contact lenses will be selected by the investigator according to the randomization table [REDACTED] for insertion by the subjects. Subjects will be dispensed the lens power nearest to their refractive error requirement.
- Lenses should be allowed to settle for 10 minutes.
- An initial fit assessment will be made to ensure lens fit is acceptable (Y/N). The subject should be discontinued and exited if the lens fit is found unacceptable and the primary reason for poor fit recorded on the CRF and video footage of the fit collected.
- Monocular spherical over-refraction (SOR) will be conducted to determine if a different lens power is required.
- Monocular and binocular **HIHC** and **HILC** distance logMAR visual acuities will be recorded (SOR will be used if the subject is wearing monovision).
- Final lenses will be inserted and allowed to settle for a further 10 minutes, if applicable.
- Subjective responses will be collected per the Post-Settling Questionnaire [REDACTED], including:
  - [REDACTED]
  - [REDACTED]
  - [REDACTED]
  - [REDACTED]
  - [REDACTED]
  - [REDACTED]
  - [REDACTED]
  - [REDACTED]
  - Lens movement/awareness (5-point Likert scales)
  - Vision (7-point Likert & 100-point scales)
- Lens surface will then be assessed and graded after settling per guidelines detailed in the CVI grading scales [REDACTED]
  - [REDACTED]
  - Wettability (0-4 scale)
  - [REDACTED]
  - [REDACTED]

- Lens fit will then be assessed and graded according to the guidelines detailed in CVI Grading scales ( [REDACTED] ).
  - Lens centration (0.1mm steps)
  - [REDACTED]
  - Post-blink movement (0.1mm steps)
  - Mobility rating (0.50 steps)
  - Overall lens movement (-2 to +2 scale)
  - Overall lens fit acceptance and investigator reason, if unacceptable (0.25 steps).  
Video will be recorded in the event of poor fit.
- The subject will be instructed to wear the study lenses for a minimum of 8 hours per day / 6 days per week.
- The subject will be dispensed adequate lenses (including spares) to last them until the next study visit.
- The subject will be discharged and scheduled to return for Visit 3 within the required study visit window.

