**Table 2: Summary of Visits and Procedures**

	Visit 1a Screening / Baseline	Visit 1b Dispense Pair 1	Visit 2 2-week follow-up Pair 1 & Dispensing of Pair 2	Visit 3 2-week follow- up Pair 2 & Exit
Informed consent	✓	-	-	-
Meet inclusion/exclusion criteria	✓	-	-	-
History at baseline	✓	-	-	-
Demographics	✓	-	-	-
Wearing time	✓	-	✓	✓
HVID / palpebral aperture size	-	✓	-	-
Auto-refraction & keratometry	✓	-	-	-
Sphero-cylindrical refraction	✓	-	-	-
HIHC & HILC VAs with sphero-cylindrical refraction	✓	-	-	-
Slit lamp biomicroscopy	✓	✓*	✓	✓
Instillation of lens at office	-	✓	✓	-
Subjective assessments	-	✓	✓	✓
Lens surface assessments	-	✓	✓	✓
Lens fit assessments	-	✓	✓	✓
Spherical over-refraction (SOR)	-	✓	✓	-
HIHC & HILC Distance VAs (with CLs)	-	✓	✓	✓
Lens Preference Questionnaire	-	-	-	✓
Exit VAs	-	-	-	✓
Study Exit	-	-	-	✓

\* Not applicable if Visit 1b occurs on the same day as Visit 1a

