### 10.1 Sample size

---

Based on historical data, a sample size of 14 completing subjects is sufficient to detect a non-inferiority margin of 0.1 logMAR for the primary variable, visual acuity, assuming  $\alpha=0.05$  and a power of 80% (Table 3).

Table 3: Primary variable (acuity) sample size calculation

Non-inferiority margin for logMAR visual acuity	Mean individual standard deviation	Sample size, Power 80% ( $p = 0.05$ )
-0.1	0.07	14

Based on historical data, a sample size of 53 completing subjects is sufficient to detect a non-inferiority margin of -0.75 for the secondary variable, comfort, assuming  $\alpha=0.05$  and a power of 80% (Table 4).

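### For monovision wearers, distance acuity follows one over-refraction rule at dispensing and another at two weeks, leaving the near eye uncorrected at follow-up

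*Combined protocol and SAP*

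**What the plan says.** The inclusion criteria in 7.1 admit monovision wearers ("monovision acceptable, but not monofit") up to age 55. Section 2 names vision as the primary variable, and 10.1 specifies it as logMAR visual acuity.

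Monocular and binocular distance acuities with study lenses are recorded four times:

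- **Dispensing of Pair 1 (7.3.2) and of Pair 2 (second part of 7.3.3).** A monocular over-refraction is done for every subject to check lens power. For the acuity reading, "SOR will be used if the subject is wearing monovision". No eye is singled out.
- **Two-week follow-up of Pair 1 (7.3.3) and of Pair 2 (7.3.4).** The same acuities are recorded, but "a spherical over-refraction will be performed for the distance eye and recorded first if the subject is wearing monovision". The near eye is not mentioned.

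Table 2 ticks over-refraction at Visits 1b and 2 and shows it as not done at Visit 3. Section 10.2 plans repeated-measures ANOVA or paired analysis across visits, includes all evaluated participants, and has no rule for monovision near eyes.

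**The concern.** In monovision the distance eye is already set for distance; the near eye is not. An over-refraction is needed to make the near eye's distance acuity informative about the lens. The follow-up text assigns it to the other eye. Two things follow:

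- The near eye's two-week distance acuity is part of the primary variable as recorded, yet it says little about the lens.
- If the dispensing reading corrects the near eye and the two-week reading does not, a between-visit comparison shows a worsening produced by the measuring procedure. At Visit 2 both rules apply on the same day, first to Pair 1 and then to Pair 2.

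The plan does not say whether the primary acuity is monocular or binocular, at which contrast level, or at which visit. Nothing later in the plan keeps these readings out of the analysis.

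**Working it through.** **The plan's own figure.** Section 10.1 states that "a sample size of 14 completing subjects is sufficient to detect" the 0.1 logMAR margin. Table 3 gives 0.07, labelled "Mean individual standard deviation". A two-arm formula at one-sided 0.05 and 80% power returns the 14: 2 × (1.645 + 0.842)² × 0.07² / 0.1² = 6.06, rounded up to 7 per arm, 14 in total. A paired calculation taking the SD of the difference as 0.07 × √2 = 0.099 needs 8 (one-sided 0.05) or 10 (one-sided 0.025). The present point does not depend on which was meant.

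**The rules side by side**

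| Measurement | Over-refraction for monovision | Near eye |
|---|---|---|
| Pair 1 dispensing (7.3.2) | Used, no eye named | Covered on the natural reading |
| Pair 1 two weeks (7.3.3) | Distance eye | Uncorrected |
| Pair 2 dispensing (7.3.3) | Used, no eye named | Covered on the natural reading |
| Pair 2 two weeks (7.3.4) | Distance eye | Uncorrected |

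Reading down a lens, the rule changes between dispensing and two weeks. Reading across lenses at the same stage, it does not.

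**Between-visit shift.** Let f be the monovision share and L the near eye's loss in logMAR when uncorrected. The documents give neither, so both are assumed. One eye of two is affected in a fraction f of subjects, so the two-eye mean shifts by f × L / 2:

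- f = 5%, L = 0.1: 0.05 × 0.1 / 2 = 0.0025 (about 0.003)
- f = 20%, L = 0.3: 0.20 × 0.3 / 2 = 0.03
- f = 30%, L = 0.5: 0.30 × 0.5 / 2 = 0.075

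**Test-Control difference at two weeks.** A near-eye loss L that is the same in both periods enters both lenses' readings, and L − L = 0 within subject. Only reading-to-reading variation in the defocused eye remains. Let s be the assumed extra SD per near-eye reading. For the two-eye mean, the SD of the difference is √(2 × 0.07² + f × 2s²/4):

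- f = 10%, s = 0.10: √(0.0098 + 0.0005) = 0.102; paired N = 11 at one-sided 0.025
- f = 30%, s = 0.15: √(0.0098 + 0.003375) = 0.115; paired N = 13

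Both are far below the roughly 60 planned completers, and power at 60 is above 99%.

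A harsher check looks only at the eye group containing the near eyes. With 20% monovision and an SD of 0.20 in those eyes, √(0.8 × 0.07² + 0.2 × 0.20²) = 0.109. Even if this is multiplied by √2, the paired N is 17 (one-sided 0.05) or 21 (one-sided 0.025), and power at 60 is above 99.8%.

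**The case against.** The strongest reply is that this is a wording inconsistency with no effect on the trial's main question. Much of that stands.

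- **Bias between lenses.** A reader might infer that the primary comparison is biased. The documents do not support that: the follow-up wording is identical for both lenses in a within-subject crossover, so a constant loss cancels.
- **Comparison with the 0.1 margin.** It is tempting to set the between-visit shift against the margin. The margin and the primary hypothesis concern Orion against Gemini, and no hypothesis is stated about change from dispensing to two weeks, so the two quantities are not comparable.
- **Table 2.** A reader might infer that Pair 1 would be followed up with over-refraction and Pair 2 without. The Visit 2 column also covers the dispensing of Pair 2, where over-refraction is routine, and that explains the tick. What remains is the omission at Visit 3 of a step that 7.3.4 requires.
- **Wording limits.** The follow-up text says the over-refraction is performed and recorded first, not that acuity is read through it, so it cannot be said that the distance eye is measured differently from other subjects' eyes. The near eye is uncorrected on either reading. That the dispensing over-refraction covers the near eye is the natural reading, not an explicit statement.
- **Extent of defocus.** Sections 7.3.2 and 7.3.3 have subjects receive the available power closest to their refractive need, which could be read as correcting both eyes for distance. But all four acuity instructions provide for a subject wearing monovision, so the plan foresees it. How far the near eye is defocused is undocumented.

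None of this removes the change of rule between dispensing and follow-up, or the uncorrected near eye at two weeks.

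**Conclusion.** The point holds as a measurement problem limited to monovision subjects. Their near-eye acuities at two weeks carry little information about the lens, and the between-visit acuity comparison in 10.2 mixes two measuring rules. With assumed shares of 5-30% and losses of 0.1-0.5 logMAR, the artificial shift in the two-eye mean is about 0.003-0.075 logMAR. This rests on the dispensing over-refraction covering the near eye. If it does not, the near eye is uncorrected at all four measurements and the between-visit shift disappears, but the readings remain uninformative.

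There is no demonstrated bias in the Test-Control difference and no threat to its power. The sample size needs no change on this account. Because the primary variable is affected and the correction is nearly free, the plan should still be changed.

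**What to change.** - **Preferred.** Reconcile 7.3.2, both parts of 7.3.3, and 7.3.4 to one rule for all four lens-acuity measurements: in monovision subjects, the near eye's distance acuity and the binocular distance acuity are read through the near eye's distance over-refraction, and the distance eye is measured as in all other subjects. In Table 2, mark over-refraction at Visit 3 for monovision subjects only. The cost is wording in the visit sections and one table cell; an over-refraction is already performed at these visits, so the added site work is minimal.
- **Alternative with no site change.** State in 10.2 that monovision near eyes are left out of the monocular distance-acuity comparisons. This loses one eye's monocular data for each monovision subject and does not deal with binocular acuity.
- **In either case.** Reconcile the power-selection wording in 7.3.2 and in the Pair 2 dispensing part of 7.3.3 with the references to subjects wearing monovision, so that it is clear how the study lenses are meant to be worn when acuity is read.
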